3.3.2. Follow-up for withdrawn subjects

Follow up by routine standard of care treatment. The intervention of this study is limited and has no lasting effects therefore long term follow up is not required. Individuals that are withdrawn from the study will continue treatment and follow up visits consistent with standard of care. Currently there is no anticipated need to replace individuals withdrawn from the study as there will be concurrent active recruitment.

4. Recruitment Methods

4.1. Identification of subjects

Identified from pool of patients who will already be undergoing with planned flexible bronchoscopy and/or endobronchial ultrasound by an interventional pulmonologist in the operating room setting. They will be identified by review of the operating room schedule and through the interventional pulmonology clinic.

4.2. Recruitment process

Once potential subjects are identified from interventional pulmonology clinic or operating room schedule by the interventional pulmonology attending, patients will be evaluated and recommendations given prior to and independent of study enrollment. Individuals that meet inclusion criteria during in person questioning will be referred to a study team member. The team member will review the case and determine eligibility. If eligible, the team member will review the study with the subject, and obtain consent.

4.3. Recruitment materials

None.

4.4. Eligibility/screening of subjects

Not applicable.

5. Consent Process and Documentation

5.1. Consent Process

5.1.1.Obtaining Informed Consent

5.1.1.1.Timing and Location of Consent

For outpatients, consent for this study will be obtained on Penn State Hershey Medical center premises, at the interventional pulmonology clinic. Consent will be obtained immediately following a patient's medical office visit, by an authorized study team member. Consents will be obtained during normal clinic business hours. During clinic hours, translation services and impartial witnesses are available. Family members typically attend clinic visits and will be encouraged to participate in the consent process.

For inpatients, consent for this study will be obtained in their designated hospital room the day before their scheduled procedure. Consent will be obtained by an authorized study team member. Floor nurses as well as visiting family members will be available as impartial witnesses and will be encouraged to participate in the consent process.

For outpatients not previously seen in clinic, consent will be obtained in the preoperative care unit the day of the scheduled procedure. Consent will be obtained by an authorized study team member. Family who are accompanying patient for procedure will be encouraged to participate in the consent process.

5.1.1.2. Coercion or Undue Influence during Consent

Consent will be obtained by the interventional pulmonologist who will be performing the procedure. Nursing staff is readily available in the clinic, medical floor and preoperative area for witness of consent. It will be explicitly stated that the care will not deviate from standard of care, and consent or abstention to this study will not affect the procedure they will receive, nor the level of medical care. If at any point the study subject expresses concern or unwillingness to proceed than the consent process will be terminated, not included in the study and explained that the same standard of care will be provided regardless.

The current IRB approved consent form will be used. Consent will be obtained following clinic visit in outpatient setting, after interventional pulmonology consult in inpatient setting and after procedure consent in pre-operative area, allowing detachment of the study and the medical care received. Patients are encouraged to have family members and other representatives present and will also be encouraged to stay for consent of the study. Questions will be encouraged, and answered adequately. Time will be given if the individual desires to discuss with family members or others. Voluntary enrollment will be explicitly stated. There are many Penn State employees that will be available as impartial witnesses I all three settings. Penn State translation services are available for non-English speaking individuals. If at any point the individual communicates they do not want to take part in the study, the consent process will immediately terminate.

5.1.2. Waiver or alteration of the informed consent requirement

Partial waiver will be obtained as per section 6.2 and 6.3.

5.2. Consent Documentation

5.2.1. Written Documentation of Consent

Written documentation of consent will be on the IRB approved consent form, and in an understandable language for the individual. The individuals name will be printed on page 1 of the form, and the person or representative will print, sign and date the consent form. The study team member obtaining consent will also print, sign and date, as well as the impartial witness. Finally a copy of the signed and dated consent will be given to the individual or representative and uploaded into the electronic medical record.

5.2.2. Waiver of Documentation of Consent (Implied consent, Verbal consent, etc.)

Not applicable.

5.3. Consent – Other Considerations

5.3.1. Non-English Speaking Subjects

This study does not specifically target non-English speaking populations. If non-English speaking individuals are encountered, current IRB approved non-English short forms will be used for Spanish, Vietnamese, Russian, Italian, and French. The study team members obtaining consent will use English and translation performed to the desired language by the Penn State translation services.

5.3.2. Cognitively Impaired Adults

5.3.2.1. Capability of Providing Consent

Capacity will be determined at time of consent for procedure. If they do not have the capacity to consent for procedure, they will not be able to consent for the research study.

5.3.2.2.Adults Unable To Consent

Not applicable.

5.3.2.3. Assent of Adults Unable to Consent

Not applicable.

5.3.3. Subjects who are not yet adults (infants, children, teenagers)

5.3.3.1.Parental Permission

Not applicable.

5.3.3.2. Assent of subjects who are not yet adults

Not applicable.

6. HIPAA Research Authorization and/or Waiver or Alteration of Authorization

6.1.	Authorization and/or Waiver or Alteration of Authorization for the Uses and Disclosures of PHI				
	Check a	All that apply: Not applicable, no identifiable protected health information (PHI) is accessed, used or disclosed in this study. [Mark all parts of sections 6.2 and 6.3 as not applicable]			
		Authorization will be obtained and documented as part of the consent process. [If this is the only box checked, mark sections 6.2 and 6.3 as not applicable]			
		Partial waiver is requested for recruitment purposes only (Check this box if patients' medical records will be accessed to determine eligibility before consent/authorization has been obtained). [Complete all parts of sections 6.2 and 6.3]			
		Full waiver is requested for entire research study (e.g., medical record review studies). [Complete all parts of sections 6.2 and 6.3]			
	U (verbal	Alteration is requested to waive requirement for written documentation of authorization authorization will be obtained). [Complete all parts of sections 6.2 and 6.3]			
6.2.	Waiver or Alteration of Authorization for the Uses and Disclosures of PHI				
	6.2.1. Access, use or disclosure of PHI representing no more than a minimal risk to the privacy of the individual				
	6.2.1.1.Plan to protect PHI from improper use or disclosure				
		Information is included in the "Confidentiality, Privacy and Data Management" section of this protocol.			
		6.2.1.2. Plan to destroy identifiers or a justification for retaining identifiers			
		Identifier will be retained through course of study as consent forms must be collected and stored.			
	6.2.2 use of	Explanation for why the research could not practicably be conducted without access to and PHI			
		Information must be obtained from the subject's electronic medical record during recruitment to determine eligibility and, in some cases, to confirm information discussed with the subject in regards to their medical history.			
		.Explanation for why the research could not practicably be conducted without the waiver or tion of authorization			

The waiver is requested only for recruitment to determine subject eligibility to ensure that no medical conditions that fall into the exclusion criteria are present and would thus preclude enrollment. This waiver will minimize the enrollment of subjects' who may ultimately fail to meet the study inclusion/exclusion criteria.

6.3. Waiver or alteration of authorization statements of agreement

Protected health information obtained as part of this research will not be reused or disclosed to any other person or entity, except as required by law, for authorized oversight of the research study, or for other permitted uses and disclosures according to federal regulations.

The research team will collect only information essential to the study and in accord with the 'Minimum Necessary' standard (information reasonably necessary to accomplish the objectives of the research) per federal regulations.

Access to the information will be limited, to the greatest extent possible, within the research team. All disclosures or releases of identifiable information granted under this waiver will be accounted for and documented.

7. Study Design and Procedures

7.1. Study Design

Patient is identified and consent is obtained in clinic, hospital room or pre-operative area. In the Same Day Pre-Anesthesia Care Unit they will receive Robitussin DM 20 ml syrup orally (Dextromethorphan 20mg) at least 60 minutes prior to bronchoscopy.

Once in the main procedure room patients will be induced into an anesthetic state using the following medications and dosing ranges. It will be titrated by anesthesiologist at bedside with goal to achieve hypnosis and apnea without profound bradycardia. The duration of the infusion is as required for the duration of the procedure.

- Propofol (1-3 mg/kg bolus and infusion of 50-200 mcg/kg), fentanyl 25-50 mcg on induction and alfentanil as a continuous infusion will be given at a rate of 0.5-2 mcg/kg/min with 1-3 mcg/kg bolus every 2-5min if need for further cough suppression. The Propofol infusion will be titrated to maintain BIS values between 40-60 for the duration of the procedure. When it is anticipated that the procedure will conclude within the next 10 minutes, the Propofol and alfentanil infusions will be stopped.

Contingency Plan: If despite the maximum dose of Propofol (150 mcg/kg/min) and alfentanil the patient continues to cough such that the procedure cannot be carried out, then Rocuronium will be administered IV (dose 20-40 mg at the discretion of the anesthesiologist) and its residual effect will be reversed using neostigmine (20-70 mcg/kg) and glycopyrrolate (10 mcg/kg) at the end of the procedure.

The patient's airway will be managed using a laryngeal mask airway (LMA) (Ambu Aura-I Size 4 or 5). Their airways will be anesthetized using a maximum of 2 mg per kg (max dose 160mg) of lidocaine, administered by one of the following techniques below. Randomization will be completed by selection of unmarked envelope.

- 1. "Spray as you go" 16mL of 1% lidocaine sprayed in 4 mL aliquots. One at the vocal cords, one at midtrachea, one at left main stem bronchus and one at right mainstream bronchus.
- 2. Nebulizer 2 % (preservative free) lidocaine (dose 2mg/kg max dose 160 mg) will be administered via a jet nebulizer, in the operating room over ten minutes, followed by procedure immediately after. The patient will be sitting propped up and his SpO2, EKG and BP will be monitored during this time. The jet nebulizer supply tube will be connected to central oxygen at 6 L/min and the duration of nebulization will be dryness of the nebulizing chamber or max of 10 minutes. [The Salter Series Small Volume Jet Nebulizer will be used.]
- 3. Vibrating Mesh Nebulizer 2 % (preservative free) lidocaine (dose 2mg/kg max dose 160 mg) will be administered via a vibrating mesh nebulizer, in the operating room over ten minutes, followed by procedure immediately after. The patient will be sitting propped up and his SpO2, EKG and BP will be monitored during this time. The jet nebulizer will be

connected to central oxygen at 6 L/min and the duration of nebulization will be dryness of the nebulizing chamber or max of 10 minutes. [The Aerogen Solo Vibrating Mesh Nebulizer will be used.]

Patient will undergo scheduled procedure of flexible bronchoscopy or endobronchial ultrasound examination. During procedure, bronchoscopist and anesthesiologist will count the number of episodes of cough. Cough is defined as a cough which requires intervention such as additional dose of anesthetic or requires a pause in the procedure. During procedure, BIS monitor average, number of vasopressor interventions for MAP <60, induction time, procedure time and wake up time will be documented in the research record.

Following procedure, patient will be brought to post-op anesthesia care unit. Time to discharge readiness will be collected as well as the responses of the patient to the following questions:

- sore throat: absent, mild, moderate, severe
- cough: absent, mild, moderate, severe

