2.3. Study Rationale

While the procedures of flexible bronchoscopy and endobronchial ultrasound is commonly performed to assess a wide range of lung disease, studies evaluating the mode of administration of topical lidocaine to prevent coughing and improve efficiency of the procedure have not yet been completed. We propose a prospective, randomized, stratified sampling, open label study of topical vs nebulized vs atomized lidocaine during flexible bronchoscopy and endobronchial ultrasound. Postoperative outcome assessors will be blinded to intraoperative therapy. We propose to evaluate the different modes of administration of topical lidocaine and their effect on the number of severe coughs as per anesthesia and the bronchoscopist, total dosing of anesthesia, post-procedure cough and sore throat and complications related to lidocaine.

As there have been no studies in regards to the mode of lidocaine application in bronchoscopy, our study is a feasability study to identify if a difference is present between nebulized and topical groups. If one is identified, we will plan to determine number needed to power a future superiority study.

Inclusion and Exclusion Criteria

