7.4.3. Method for Assigning Subject to Treatment Groups

Subject forms will have administration mode documented and will be placed in sealed envelopes. Immediately prior to procedure, envelope will be opened to determine which mode of lidocaine administration will be performed. [name] will secure all envelopes within locked cabinet in [name]'s office. Subject will be told of their assigned treatment group. Inpatient/Outpatient will be a 50/50% stratification.

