7.4.6.3. Preparation and Dispensing

Mode of administration will be determined day of procedure by selection of randomized, sealed envelopes containing subject form with administration mode. The atomized and nebulized lidocaine will be prepared and administered by the anesthesiologist. The "spray as you go" lidocaine will be prepared by the scrub nurse and administered by the bronchoscopist. Preparation involves loading medication into administration devices.

Medication will not be dispensed directly to subject.

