8.1. Number of Subjects

48 patients randomly assigned to lidocaine application technique (24 in topical, 12 in jet nebulizer and 12 in vibrating mesh nebulizer). Among each group there will be stratification of flexible bronchoscopy/endobronchial ultrasound procedures and inpatient/outpatient.

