8.2. Sample size determination

Not applicable.

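### The envelope draw describes no step that delivers the two-factor stratification promised in 8.1, and 7.4.3 names only one of the two factors

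*Combined protocol and SAP*

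**What the plan says.** Four sections bear on allocation.

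- Section 8.1 fixes the arms: "48 patients randomly assigned to lidocaine application technique (24 in topical, 12 in jet nebulizer and 12 in vibrating mesh nebulizer"). It adds: "Among each group there will be stratification of flexible bronchoscopy/endobronchial ultrasound procedures and inpatient/outpatient".
- Section 7.4.3, which covers assignment, names one factor: "Inpatient/Outpatient will be a 50/50% stratification". On the mechanism it says: "Subject forms will have administration mode documented and will be placed in sealed envelopes". The envelopes are kept in a locked cabinet and opened just before the procedure.
- Section 7.1 gives the draw itself: "Randomization will be completed by selection of unmarked envelope".
- Section 7.4.6.3 says: "Mode of administration will be determined day of procedure by selection of randomized, sealed envelopes containing subject form with administration mode".

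No section mentions separate envelope sets per stratum, sequence numbers, blocks, how the 2:1:1 order is generated, or an opening log. Nor does any section say whether the envelopes form one fixed pool of 48. Sections 8.3 and 10.7 plan medians, interquartile ranges and percentages, with no adjustment for either factor.

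**The concern.** Stratification happens only if the patient's stratum determines which envelope is opened. The text describes a selection from envelopes that carry no marking, and no step that ties the selection to a stratum or an order. A team following it literally could run an unstratified draw and believe it had met 8.1. A team following 7.4.3 would stratify on inpatient status and leave procedure type to chance.

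The sponsor chose both factors, and both could plausibly affect cough and drug use, although the documents do not quantify this. Each nebulizer arm has only 12 patients, so a shift of three on either factor changes its make-up noticeably. Because the analysis is unadjusted, the allocation is the only described protection. Section 2.3 intends to use any difference between nebulized and topical lidocaine to size a later superiority trial, so an imbalance could carry into that calculation.

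**Working it through.** **Inputs.** From 8.1: N = 48, arms 24/12/12, two factors. From 7.4.3: 50/50 on inpatient status, read as 24/24. Assumed, because not stated: 24/24 on procedure type, four crossed strata of 12, no withdrawals, and one fixed pool drawn without replacement.

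**1. The plan's totals.** 24 + 12 + 12 = 48. A fixed pool of 48 envelopes gives exactly 24/12/12. This is the favourable reading: independent draws at 2:1:1 would hit those totals with probability 48!/(24!·12!·12!) × 0.5^24 × 0.25^24 = 1.8%.

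**2. What stratification would give.** Each stratum of 12 at 2:1:1 holds 6/3/3. Over four strata: 4×6 = 24, 4×3 = 12, 4×3 = 12. Each nebulizer arm then has 2×3 = 6 inpatients and 6 patients of each procedure type.

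**3. One nebulizer arm, one factor, single pool.** The number of inpatients X in the arm is hypergeometric: P(X = x) = C(24,x)·C(24,12−x)/C(48,12).

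- P(3) = 0.0380, P(2) = 0.0078, P(1) = 0.0009, P(0) = 0.00004; sum 0.0467.
- By symmetry, a split of 9:3 or worse has probability 2 × 0.0467 = 9.3%.
- The arm falls wholly in one level with probability 2 × 0.00004 = 0.008%.

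**4. Either nebulizer arm, one factor.** With a and b the inpatient counts in the two arms, sum P(a)·P(b given a) over outcomes where either count is at most 3 or at least 9. The second term is hypergeometric with 36 patients left, 24−a of them inpatients, and 12 drawn. Result: 17.2%. The two arms differ from each other by four or more inpatients with probability 15.6%.

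**5. Either nebulizer arm, at least one of two factors.** A simulation of 100,000 random permutations gives 31.5%. As a rough check, treating the factors as independent gives 1 − (1 − 0.172)² = 31.4%.

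**6. If only inpatient status is stratified, as 7.4.3 reads.** A procedure-type split of 9:3 or worse in at least one nebulizer arm remains about 18% likely (50,000 simulated allocations).

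**7. Range for the assumed mix.** The probability that a given nebulizer arm is three or more patients from its expected count is:

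| Split of the factor over 48 patients | Probability |
|---|---|
| 24/24 | 9.3% |
| 16/32 | 7.3% |
| 12/36 | 4.9% |

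The chance falls as the mix becomes more uneven, but does not vanish.

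**The case against.** The strongest reply is that silence is not a defect in conduct. The word unmarked may mean only that the outside does not reveal the arm, which is ordinary concealment. Unmarked envelopes kept in separate stacks per stratum would be consistent with 7.1, 7.4.3, 7.4.6.3 and 8.1 together. This is also a feasibility study with a descriptive analysis and no planned test, and imbalance could be displayed in the tables. All of that is fair. It limits the point to an unspecified mechanism and two sections that disagree.

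Four stronger readings are tempting, and the documents do not support them.

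- *The draw cannot produce the stated allocation.* A fixed pool does give 24/12/12, and separate stacks could stratify.
- *No order of opening is recorded.* The text describes no log, but it does not say that none will be kept.
- *The small arms may be confounded with procedure type or setting.* What is at issue is chance imbalance. An arm falling wholly in one level of a balanced factor has probability 0.008%.
- *The pool is too easy to guess.* Suppose staff always guess the most frequent remaining arm and know the remaining counts. They are then right on average 53% of the time with one pool of 48, against 60% with 2:1:1 blocks of 8 and 65% with blocks of 4. Predictability argues for the single pool, not against it.

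**Conclusion.** The point holds as a gap between promise and mechanism. Sections 7.4.3 and 8.1 name different stratification factors, and no described step connects a stratum to an envelope. On the single-pool reading, the arm totals are safe and the stratification is absent: about a 17% chance that a nebulizer arm splits 9:3 or worse on inpatient status, and about 31.5% on at least one factor. These figures rest on one fixed pool, 24/24 on each factor, four strata of 12 and no withdrawals. Only the inpatient split has support in the text. Section 3.3.2 anticipates no replacement of withdrawn patients, so final numbers can drift from 24/12/12 under any scheme. The amendment is worth making because it is cheap and delivers the design the protocol already claims.

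**What to change.** In 7.1 and 7.4.3, replace the unmarked-envelope draw with a computer-generated 2:1:1 list for each of the four strata (procedure type by inpatient or outpatient). The custodian holds four separate sets of opaque sealed envelopes. Each is marked outside with stratum and sequence number, with the arm not visible, and is opened strictly in order and logged. Name both factors in 7.4.3, and say whether its 50/50 is a recruitment quota.

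Then choose one of two schemes and state it:

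- **Strata capped at 12.** Use one random permutation of 6/3/3 per stratum. The totals are exactly 24/12/12 and 48 envelopes suffice.
- **Strata not capped.** Use undisclosed varying blocks, for example 4 and 8, prepare surplus envelopes, and state that the totals are approximate. With blocks of 4 and stratum sizes varying randomly around 12, the totals equal 24/12/12 in only about 26% of simulations.

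The cost is a short amendment, envelope preparation, four stacks and a log. No extra patients or staff are needed. The price in an open-label trial is a somewhat more predictable next assignment than with one large pool, which is why block sizes should vary and stay undisclosed.

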7.4. Test Article(s) (Study Drug(s) and/or Study Device(s))

7.4.1.Description

160mg of 1% lidocaine is approved by the FDA for anesthetizing tracheobronchial tree. The mode of administration (spray as you go vs nebulized vs atomized) has been shown to have similar safety profile however efficacy has not been determined.

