7.4.2. Treatment Regimen

Their airways will be anesthetized using 160mg of lidocaine, administered by one of the following techniques:

- 1. "Spray as you go" 16mL of 1% lidocaine sprayed in 4 mL aliquots. One at the vocal cords, one at midtrachea, one at left main stem bronchus and one at right mainstream bronchus.
- 2. Jet Nebulizer 8 mL of 2 % lidocaine administered via a jet nebulizer over ten minutes, followed by procedure immediately after.
- 3. Vibrating Mesh Nebulizer 8 mL of 2 % lidocaine administered via a vibrating mesh nebulizer over ten minutes, followed by procedure immediately after.

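### Sections 7.1 and 7.4.2 give conflicting lidocaine doses below 80 kg, and under one reading the spray and nebulizer arms are loaded with different amounts of drug

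*Combined protocol and SAP*

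**What the plan says.** Section 7.1 (Study Design) opens the lidocaine instructions with a limit that precedes all three techniques: "Their airways will be anesthetized using a maximum of 2 mg per kg (max dose 160mg) of lidocaine". The three items that follow do not treat weight in the same way.

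- Spray: "16mL of 1% lidocaine sprayed in 4 mL aliquots", one aliquot at each of four sites. No mg/kg term and no reduced volume are given.
- Jet nebulizer: "lidocaine (dose 2mg/kg max dose 160 mg) will be administered via a jet nebulizer".
- Vibrating mesh nebulizer: "lidocaine (dose 2mg/kg max dose 160 mg) will be administered via a vibrating mesh nebulizer".

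Section 7.4.2 (Treatment Regimen) drops weight altogether: "Their airways will be anesthetized using 160mg of lidocaine, administered by one of the following techniques". It lists the same 16 mL of 1% for spray and 8 mL of 2% for each nebulizer. Section 7.4.1 also refers to a fixed amount: "160mg of 1% lidocaine is approved by the FDA for anesthetizing tracheobronchial tree".

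The entry criteria in sections 3.1 and 3.2 set a lower age limit but no weight limit. Section 11 says that only the way the drug is delivered will vary between patients. Section 2.3 gives the purpose as "to identify if a difference is present between nebulized and topical groups" and, if one is found, to size a later superiority study.

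**The concern.** For a patient under 80 kg, the spray item and section 7.4.2 both call for more lidocaine than the section 7.1 limit allows, and nothing in the protocol ranks the two sections. Three readings are open:

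- **A.** The section 7.1 limit governs every arm.
- **B.** Section 7.4.2 governs and everyone receives 160 mg.
- **C.** Each section 7.1 item is followed on its own terms: spray at 160 mg, nebulizers at 2 mg/kg.

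Under A and B the nominal dose is the same in every arm. Under C it is not, and the larger dose always goes to spray. Lighter patients would then contribute a comparison of mode and dose together to the contrast named in section 2.3, contrary to section 11.

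The division of work makes C plausible. Under section 7.4.6.3, the scrub nurse prepares the spray and the bronchoscopist gives it, while the anesthesiologist prepares and gives the nebulized drug. Each could follow the item for their own arm.

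The plan would not reveal the problem. The data items listed in sections 7.1 and 16.1 name neither body weight nor the lidocaine dose given, and the analysis in sections 8.3 and 10.7 is descriptive, with no adjustment.

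**Working it through.** **Inputs.** Limit of 2 mg/kg, at most 160 mg (7.1). Spray 16 mL of 1%, i.e. 10 mg/mL (7.1 and 7.4.2). Nebulizer 2 mg/kg, at most 160 mg (7.1), or 8 mL of 2%, i.e. 20 mg/mL (7.4.2). The protocol gives no weight distribution, so the weights below are illustrative.

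**The plan's own figure.** Spray: 4 × 4 mL × 10 mg/mL = 160 mg. Nebulizer: 8 mL × 20 mg/mL = 160 mg. The flat 160 mg of section 7.4.2 is reproduced in every arm.

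**Where the rules part.** 2 mg/kg reaches 160 mg at 160/2 = 80 kg. From 80 kg up all readings give 160 mg; below it they diverge.

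**Loaded dose by reading.** Capped dose = min(2 × weight, 160). Flat dose per kg = 160/weight.

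| Weight | A: spray v nebulizer | B: spray v nebulizer | B in mg/kg | C: spray v nebulizer | C: difference (ratio) |
|---|---|---|---|---|---|
| 50 kg | 100 v 100 mg | 160 v 160 mg | 3.20 | 160 v 100 mg | 60 mg (1.60) |
| 60 kg | 120 v 120 mg | 160 v 160 mg | 2.67 | 160 v 120 mg | 40 mg (1.33) |
| 70 kg | 140 v 140 mg | 160 v 160 mg | 2.29 | 160 v 140 mg | 20 mg (1.14) |
| 80 kg | 160 v 160 mg | 160 v 160 mg | 2.00 | 160 v 160 mg | 0 mg (1.00) |

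**Volumes needed if the limit is meant.** Spray mL = dose/10; aliquot = dose/40; nebulizer mL = dose/20.

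| Weight | Spray | Each of four aliquots | Nebulizer |
|---|---|---|---|
| 50 kg | 10 mL | 2.5 mL | 5 mL |
| 60 kg | 12 mL | 3.0 mL | 6 mL |
| 70 kg | 14 mL | 3.5 mL | 7 mL |
| 80 kg and over | 16 mL | 4.0 mL | 8 mL |

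Only the last row appears in the protocol.

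**A side note on delivered dose.** All these figures are loaded doses. Section 7.1 says that "the duration of nebulization will be dryness of the nebulizing chamber or max of 10 minutes". An 8 mL load empties in that time only if output is at least 8/10 = 0.8 mL/min, and a 5 mL load only at 0.5 mL/min or more. No output rate is given, so loaded and delivered dose may differ under any reading. This is separate from the conflict between the dose rules, which does not depend on it.

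**The case against.** The best defence is that reading A is the natural one. The limit stands ahead of all three items and by grammar covers them, so 16 mL and 8 mL can be taken as the volumes at the ceiling. Section 7.2.1 also refers back to the study design for the procedure. On this view, ignoring the opening sentence in order to follow the spray item is not literal compliance with section 7.1 at all, and unequal arms arise only on the least natural reading. That operators would in fact diverge is a conjecture.

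This has weight, and it is why the confounding is stated as conditional. It does not remove the conflict. Section 7.2.1 does not say which section prevails. The nebulizer items restate the mg/kg rule and the spray item does not, and no scaled spray volume is given anywhere. If A is right, section 7.4.2 is wrong for every patient under 80 kg.

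A second argument is that equal milligrams would not equalise exposure: the arms already differ in concentration, timing and site of delivery. That is true, but those differences belong to the modes being compared. A difference in loaded dose does not, and it could be removed by drafting.

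A third is that this is a descriptive feasibility study of 48 patients in which no formal test depends on the dose rule. This limits the statistical damage. It does not excuse leaving the dose of the study drug undetermined, particularly when the result may be used to size a further trial.

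**Conclusion.** The concern holds. For patients under 80 kg the protocol contains two incompatible lidocaine rules, and its fixed spray volume conflicts with its own limit. At 50, 60 and 70 kg the flat dose exceeds the 2 mg/kg limit by 1.20, 0.67 and 0.29 mg/kg (3.20, 2.67 and 2.29, less 2). If the section 7.1 items are each followed separately, the spray arm is loaded with 60, 40 and 20 mg more than the nebulizer arms; under the other two readings the arms are equal.

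The conflict itself rests only on the protocol's text and on volume times concentration. Any effect on the comparison depends on which reading staff adopt and on how many patients weigh less than 80 kg, neither of which the documents settle. It is not claimed that 160 mg is unsafe, or that a gap of this size changes the cough count. Because the point concerns the dose of the study drug, it should be corrected before patients are treated under this text.

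**What to change.** State one mg rule, identical for all three arms, in both section 7.1 and section 7.4.2. The clinical team should choose which.

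- **If the 2 mg/kg limit is kept:** spray 0.2 mL/kg of 1%, at most 16 mL, in four equal aliquots; each nebulizer 0.1 mL/kg of 2%, at most 8 mL. Replace the flat 160 mg and fixed volumes in section 7.4.2 accordingly.
- **If a flat 160 mg is intended:** delete the 2 mg/kg terms from the opening lidocaine sentence of section 7.1 and from both nebulizer items.

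In either case, record weight and the mg and mg/kg loaded, and tabulate them by arm. Weight is already needed to dose propofol and alfentanil. Recording the nebulizer volume left at stop is a useful addition but is not needed to resolve the conflict.

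The cost is amendment text and a few fields on the subject form. If the limit is kept, lighter spray patients receive less volume at each site (2.5 mL rather than 4 mL at 50 kg), and the clinical team must be content with that.
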